• The patient will self-administer the Sitzmarks capsule (contains 24 radiopaque markers; Konsyl Pharmaceuticals, Texas, USA) by mouth with water on Days 8,9, and 10 and will consume their usual diet during this period. The patient will abstain from using suppositories or enemas until they return on Day 11. An abdominal XR will be scheduled on Day 11

Day 11 – Site Visit 2

An abdominal XR will be obtained to determine the location and the extent of elimination

of the radiopaque markers. Patients who expel at least 80% (19 or more of the markers) have

grossly normal colonic transit. If remaining markers are scattered about the colon, the condition is

most likely hypomotility or colonic inertia. If remaining markers are accumulated in the rectum or

rectosigmoid, the condition is most likely functional outlet delay. Radiographs will be collected in

electronic format and subsequently analyzed in blinded manner by a centralized reader ([name] MD, and [name], MHA, Division of Gastroenterology and Hepatology, Mayo

Clinic). The patient will be given study medication (B) and a PAC-SYM and PAC-QOL to take

home. This will trigger randomization to treatment or placebo and to PK or no PK.

Day 14- Phone call

Patients will be asked to complete the PAC+SYM and PAC-QOL questionnaires. They

will be instructed to take the medication the following morning on an empty stomach and not to

eat anything for at least 60 minutes thereafter. Baseline complete, spontaneous bowel movements

(CSBM) will be calculated from the diaries at the 14 day phone call as CSBM/entries x

7.Baseline PAC-SYM and PAC-OOL and baseline ease of passage and consistency will also be

obtained at this time-point.

PERIOD 3.2 (Stage 2): Multiple doses

Safety, tolerability and pro-kinetic effect of orally administered multiple-dose ENT-01 in

Sentinel Group followed by Remaining Cohort

Cohort 2 (40 patients, of which 10 comprise the sentinel group):

Duration: 17-19 days

The purpose of this period is to demonstrate the continued pro-kinetic effect beyond that

of a single-dose, to confirm the effective pro-kinetic dose for each individual and to establish the

safety, tolerability and PK of multiple doses of ENT-01. A pro-kinetic dose is defined as the dose

that results in a spontaneous, complete stool on at least two of the three dosing days. Once the

pro-kinetic dose is established, and assuming there are no safety concerns, each patient will be

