PK subjects will come to the site on Day 1 of randomization ON AN EMPTY STOMACH and return their unused study drug at that time point. They will receive the first dose of medication at the site following the first PK blood draw, and complete the questionnaires listed below. PKs will also be performed at 1, 2, 4, and 8 hours post-dose. A sample for liver function tests will be drawn with the 8-hour post-dose PK draw. They will receive 4 daily doses to take home, then return on Day 6 to receive their 6th dose at the site after their first PK draw of the day. PKs will again be obtained post-dose at 1, 2, 4 and 8 hours, a sample for liver function tests will be drawn with the 8-hour post-dose PK draw, and all the questionnaires completed.

Following the 5-7 day course on the pro-kinetic dose, ALL patients will be randomized to drug or placebo and enter Period 4. Randomization will be 1:1 to treatment vs. placebo. Randomization will occur in accordance with the randomization schedule generated by [name] at Weill-Cornell Medical College. Patients and study staff will be blinded to actual study treatment and will remain blinded throughout the remainder of the study. BDI, MMSE, Trail making A and B, NMSQ, UM-PDHQ, PFS-16, RBDQ, PDSS, PAC-SYM and PAC-QOL will be administered prior to randomization. The UPDRS will be administered and weight and vital signs will be taken).

Assuming randomization is to treatment group, the patient will remain on that dose daily for a 6 day period (6 dosing days). Patients randomized to placebo will be switched to the same number of placebo tablets as they were taking prior to switching. All patients will continue to keep daily diaries during this period. The use of rescue medication (suppositories and enemas) for constipation will be permitted as needed if a bowel movement has not occurred for 3 days and recorded in the diary. Patients will be contacted daily. The suppository will be taken on the evening of the third day as shown in Figure 1 above. *Any bowel movement produced as a result of rescue medication will not be counted.*

Patients reaching their tolerability limit at a dose lower than a clinically effective dose (STDE) will be terminated from the study. We have included 40 patients in this Stage to allow for 15% drop-outs for reasons including tolerability.

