Patients will wear the I-Button continuously throughout the randomized period except during bathing periods. Stool and sleep diaries will be completed daily throughout the period. BDI, MMSE, Trail making A and B, NMSQ, UM-PDHQ, PFS-16, RBDQ, PDSS, PAC-SYM and PAC-QOL will be administered on the first (Visit 3) and last day (Visit 4).

Pharmacodynamics WSW:

On Day 6 of this randomized period, patients will have a second set of motility tests (Sitzmarks capsules) to determine whether there has been any improvement in colonic motility. Patients will be compared against their own baseline motility and the placebo group will also be compared to the treatment group. The protocol will be identical to the baseline motility assessment. Patients will self-administer one capsule per day for three days beginning on Day 3 of the randomization period with subsequent capsules taken on Day 4 and Day 5. An abdominal XR will be scheduled on Day 6. Motility at the end of the randomized period will be compared with

baseline for all 40 patients and motility will also be compared between treatment and placebo groups (20 patients per group).

Safety and tolerability will be reassessed throughout the randomized treatment period. The study coordinator will call each patient at the end of each day and patients will be told to call the coordinator whenever they need to.

Summary of Stage 2, Period 4

Stage 2								6 daily	doses
PERIOD 4 Double	All cohorts,	Afte	After 4th		Randomized	PLA	CEBO		\Rightarrow
	N=40	dose at the	at the	1:1					
blinded,	IV-40	1.1		LS1	DEi				
randomized									

Pharmacokinetics and LFTs: On the randomization Day 1, 7 patients from the treatment group and 3 patients from the control group will undergo blood draws for PK analysis at pre-dose, 1, 2, 4 and 8 hours after a dose and LFTs will be obtained on the last blood draw. These same 10 patients will undergo repeat blood draws for PK analysis and LFTs during their visit to the clinical trial unit on randomization Day 6 for the abdominal x-ray and repeated patient questionnaires/surveys. Study medication will be administered by study staff on randomization Day 1 and again on Day 6 after the first blood draw.

PERIOD 5 (Stage 2): Wash-out period

Duration: 2 weeks

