9 STUDY PROCEDURES

9.1 Sitzmarks assessment of colonic motility in Stage 2

On Day 8 of the run-in period and again on Day 3 of the randomized period, patients will be reminded to self-administer a Sitzmarks capsule (contains 24 radiopaque markers; Konsyl Pharmaceuticals, Texas, USA). The patient will be instructed to abstain from using suppositories or enemas if possible until they return on Day 11 (or day 6 of randomized period). If they have to use suppositories on day 11 (or Day 6 of randomized period), make sure it's recorded in the daily diaries. An abdominal XR will be scheduled for Day 11 of run-in and Day 6 of randomized period.

On Day 11 of the run-in Period and again on Day 6 of the randomized period, an abdominal XR will be performed to determine the location and the extent of elimination of the radioisotope markers. Patients who expel at least 80% (19 or more of the markers) have grossly normal colonic transit. If remaining markers are scattered about the colon, the condition is most likely hypomotility or colonic inertia. If remaining markers are accumulated in the rectum or

rectosigmoid, the condition is most likely functional outlet delay. For patients whose markers accumulate in the rectosigmoid or when markers are retained diffusely, instruct patient to maximize liquid intake for the next two weeks.

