patients who were randomized to receive ENT-01 (between 17 and 20 patients). This analysis will consist only of those patients with assessments at baseline (end of run-in period, Period 3.1), the end of Period 4, and the end of Period 5. This analysis will have between 17 and 20 patients and will be done using an exact sign test of equality of paired proportions.

Exploratory analyses:

The first exploratory analysis will of the colonic motility values as measured by an estimate of the mean MCT times. Comparisons will be made within each patient at different time points (i.e. baseline and the end of fixed period) as well as between patient groups (i.e. values observed at the end of randomization period, period 4 for the placebo and the ENT-01 treated groups). The primary endpoint for this analysis is the MCT based on a single film estimate. From a previous study (Ashraf et al., 1997), and estimate for the average MCT for constipated patients with Parkinson's disease is 53.4 hours and an estimate of the standard deviation is 15.9 hours. A paired t-test will be used to compare the mean change in MCT at the end of the fixed period from baseline. A sample size of 34 (40) patients will have 80% power to detect a mean change of 11.1 hours (10.2 hours) with a 0.05 two-sided level of significance and using a paired t-test. This calculation assumed a conservative estimate of 22.4 hours for the standard deviation of the change in MCT, which is the square root of 2 times the variance of the baseline standard deviation. The comparison of the average MCT between the control group and the group randomized to ENT-01 at the end of the randomization period will be made with a two-group t-test.

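### The rules on suppository and enema use around the two Sitzmarks tests contradict each other, and no rule says how a rescue-affected film enters the MCT comparisons

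*Protocol*

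**What the plan says.** **Baseline test (Protocol Section 3.1, Period 3.1).** Capsules are taken on Days 8, 9 and 10 of the run-in and the film is on Day 11. The procedure text is unqualified: "The patient will abstain from using suppositories or enemas until they return on Day 11". The general run-in text in the same section allows a suppository after three consecutive days without a stool, taken on the fourth morning, with an enema if that fails. Section 4.6 also allows suppositories and enemas in the run-in. Neither passage makes an exception for the capsule days.

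**Second test (Section 3.1, Period 4).** Capsules are taken on Days 3, 4 and 5 of the randomized period and the film is on Day 6. On rescue: "The use of rescue medication (suppositories and enemas) for constipation will be permitted as needed if a bowel movement has not occurred for 3 days". On timing: "The suppository will be taken on the evening of the third day". On the test itself: "The protocol will be identical to the baseline motility assessment".

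**Both tests (Section 9.1).** Patients are to be "instructed to abstain from using suppositories or enemas if possible until they return on Day 11 (or day 6 of randomized period". It adds: "If they have to use suppositories on day 11 (or Day 6 of randomized period), make sure it's recorded".

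**Analysis.** Section 3.1 (Period 4) compares end-of-period motility with baseline in all 40 patients, and between the two groups of 20. Section 10.5 plans a paired t-test on MCT that "will have 80% power to detect a mean change of 11.1 hours (10.2 hours", and a two-group t-test between arms. The rule that discounts stools within 24 hours of rescue (Sections 4.6 and 10.3.2) applies to counted bowel movements, not to MCT.

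**SAP.** Section 1 says the SAP supersedes the protocol's statistical considerations. Sections 7.7.1 and 7.7.2 list no MCT variable. Table 3 keeps the capsules and X-rays for patients under the July 2017 protocol; Table 4, for the February 2018 amendment, shows neither.

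**The concern.** A suppository or enema can expel markers, so a film taken after rescue may show faster transit for a reason other than ENT-01. The comparison of the two films is interpretable only if rescue was governed by the same condition in both windows, or if affected films are identified and handled. Site staff reading this protocol could follow any of three instructions: abstain, abstain if possible, or use rescue as the general rule allows. Practice could then differ between sites, between windows and between arms, and the analysis text would give no guidance on the resulting films.

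What is at stake is the only measure of colonic transit in the study. It is the first exploratory objective of Stage 2 and has its own power statement.

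**Working it through.** **1. The instructions side by side.**

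| Place in protocol | Baseline window (Days 8–11) | Period 4 window (Days 3–6) |
|---|---|---|
| 3.1, Sitzmarks procedure | Abstain, no qualifier | Declared identical to baseline |
| 3.1, general rescue text | Allowed after three days without a stool; fourth morning | Allowed after three days without a stool; third evening |
| 4.6 | Allowed in the run-in | For dosing: evening of the third dose at a given level |
| 9.1 | Abstain if possible | Abstain if possible |

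Each window has both a general permission and a test-specific abstention, and the abstention has two strengths. Nothing says which text governs. In Period 4 the third evening without a stool can be Day 3, 4 or 5, all after the first capsule.

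**2. The plan's own figure.** Inputs from Section 10.5: SD of change 22.4 h, two-sided 0.05, paired t-test. With noncentrality δ/SD × √n:
- n = 34, δ = 11.1 h: 11.1/22.4 × √34 = 2.89, power 80.1%.
- n = 40, δ = 10.2 h: 10.2/22.4 × √40 = 2.88, power 80.2%.

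The stated 80% reproduces. (√2 × 15.9 is 22.49, not 22.4; using it gives 79.8% and 79.9%.) For the between-arm test the protocol states no power. With SD 15.9 h, the difference detectable with 80% power is 15.8 h at 17 per arm and 14.5 h at 20 per arm. The 10.2 to 11.1 h figures belong to the paired test only.

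**3. What rescue would do.** Let r be the hours by which rescue lowers a user's MCT, and let f_b, f_p and f_a be the proportions using rescue in the window at baseline, on placebo in Period 4 and on ENT-01 in Period 4. With 1:1 allocation:
- spurious within-patient reduction, arms pooled = r × [(f_p + f_a)/2 − f_b];
- shrinkage of the placebo-minus-ENT-01 difference = r × (f_p − f_a).

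The first depends on use at baseline; the second does not. They are separate conditions.

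**4. Illustration.** None of r, f_b, f_p or f_a is in the documents, so every value here is an assumption. The within-patient columns take f_b = 0 and n = 40; the last column takes 20 per arm and a true difference of 14.5 h.

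| r | f_p / f_a | Spurious within-patient reduction | False-positive rate (nominal 5%) | Between-arm shrinkage | Power (80% without bias) |
|---|---|---|---|---|---|
| 6 h | 20% / 10% | 6 × 0.15 = 0.9 h | 5.7% | 6 × 0.1 = 0.6 h | 77% |
| 12 h | 40% / 10% | 12 × 0.25 = 3.0 h | 13% | 12 × 0.3 = 3.6 h | 56% |
| 24 h | 60% / 20% | 24 × 0.4 = 9.6 h | 75% | 24 × 0.4 = 9.6 h | 16% |

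If baseline use equals average Period 4 use, the within-patient shift is 0 h and the false-positive rate stays at 5%. The between-arm column is unchanged.

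**5. Which comparison.** Section 3.1 sets the Period 4 film against baseline. Section 10.5 words the paired test as end of fixed period against baseline, but no film is scheduled at that point. The within-patient argument applies to the Section 3.1 comparison.

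**The case against.** A reader might infer that the protocol bars rescue at baseline and permits it in Period 4, so that the two tests are unequal by design. The documents do not support that. The inference sets the baseline test instruction against the general rescue rule of Period 4. Section 9.1, the procedure section for both tests, gives one instruction for both windows, and the run-in has its own general permission in Sections 3.1 and 4.6. What stands is contradictory wording, not a deliberately unequal rule.

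A second objection is mechanical. A suppository on the evening of Day 3 follows a capsule taken that same day, and Section 10.5 cites a mean transit of 53.4 h, so few of those markers would be within reach of rectal rescue. This is fair: large effects per use would need rescue later in the window. It weakens the upper rows of the illustration, not the finding that Days 4 and 5 are also open to rescue.

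A third is status. MCT is exploratory, the February 2018 amendment removed the randomized period, the SAP lists no MCT analysis, and SAP Section 7.7 rules out formal between-arm tests of pharmacodynamic variables. This limits the consequence. It does not close the matter: films were scheduled under the July 2017 protocol, SAP Section 5.1 says nothing has changed from the protocol's planned analyses, and SAP Section 9 names two dropped analyses, neither of them MCT.

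**Conclusion.** The point holds as an inconsistency plus a missing handling rule. Rescue can fall inside either marker window, and an affected film would enter the within-patient and between-arm MCT comparisons unmarked.

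A reader might go further and infer that the two comparisons are biased in opposite directions. That is not established. Shrinkage between arms requires more rescue on placebo than on ENT-01, and would arise even under one shared rule. Apparent improvement within patients requires more rescue in the Period 4 window than at baseline. The documents report neither pattern, no rescue rates and no effect of rescue on MCT, so neither the presence nor the size of a bias can be stated. The hours in the illustration show sensitivity to assumed inputs and are not estimates.

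The importance is modest: an exploratory measure, affecting only films taken under the July 2017 protocol. The correction is cheap.

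**What to change.** 1. Reconcile Protocol Section 3.1 (run-in rescue text, Sitzmarks procedure and Period 4), Section 4.6 and Section 9.1 so that one stated condition on suppository and enema use governs both marker windows. Which condition is for the sponsor to set.
2. For any MCT analysis of films taken under the July 2017 protocol, flag each film with diary-recorded suppository or enema use between the first capsule and the film. Tabulate flagged films by arm and time point.
3. Repeat the planned MCT comparisons without the flagged films as a sensitivity analysis. Because this selects on rescue use after randomization, it shows how far the result depends on those films and does not replace the main comparison. Giving flagged films the slowest rank is not advised: it would turn MCT partly into a measure of rescue use and, if rescue is commoner on placebo, push the between-arm result toward ENT-01.
4. State in the SAP whether MCT is analysed or dropped, and bring Sections 5.1 and 9 into line with that.

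The cost is protocol and SAP wording, one flag built from data already in the diary, and one extra exploratory analysis on fewer films.

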4 STUDY POPULATION

Patients will be selected by neurologists specializing in movement disorders from among PD patients in tertiary referral centers. Patients will have PD and constipation as defined by the inclusion criteria. PD will be diagnosed according to the UK Parkinson's Disease Society Brain Bank criteria.

4.1 Number of Patients

Roughly 50 patients will be included. Ten patients will be included in Stage 1 and 40 patients in Stage 2. Assuming a 15% drop-out rate, 8-9/10 patients will complete Stage 1 and 34/40 patients will complete Stage 2.

4.2 Selection Criteria

Patients will be selected by individual site PIs from among PD patients seen at the tertiary referral center. Patients will be screened for the presence of non-motor symptoms of PD, specifically constipation and REM behavior disorder (RBD). *The population will be enriched with respect to NMS, specifically sleep delay and sleep fragmentation problems, and RBD.* The presence of constipation at baseline will be established according to the Rome IV criteria and other inclusion criteria below. Onset of constipation before or after a diagnosis of PD will specifically be noted and its duration and severity established. The daily stool diary will be analyzed at the end of the two week run-in period to establish the presence of severe constipation on rescue medication alone (does not apply to Stage 1). Patients with two or fewer complete, spontaneous bowel movements per week will be entered into the treatment phase. RBD will be determined by history and questionnaire. The use of anti-depressants, anti-cholinergics and anti-psychotics will be permitted as long as patients are on a stable dose of medication.

4.3 Inclusion Criteria

- Patients aged 30-86 year old, both genders
- Subjects must be diagnosed with Parkinson's disease (PD), according to the UK Parkinson's Disease Society Brain Bank criteria, by a neurologist specializing in movement disorders.

- There are insufficient criteria for IBS
- Constipation which has been present for over 6 months and is unresponsive to first line, typically over the counter treatments such as milk of magnesia (1 gram), Miralax (17g in 8 ounces of water) or the equivalent at least once weekly with an inconsistent response over a 6 week period.
- Body mass index of 18-40 kg/m²
- Subjects must fulfill Rome IV criteria for functional constipation which includes 2 or more of the following:
 - Straining during at least 25% of defecations
 - o Lumpy or hard stools in at least 25% of defecations
 - Sensation of incomplete evacuation for at least 25% of defecations
 - o Sensation of anorectal obstruction/blockage for at least 25% of defecations
 - Manual maneuvers to facilitate at least 25% of defecations (e.g., digital evacuation, support of the pelvic floor)
- Fewer than 3 spontaneous, complete defecations a week.
- Loose stools are rarely present without the use of laxatives
- Patients must provide written informed consent and be willing and able to comply with study procedures.
- Patients must be able to read, understand, and accurately record data into the diary to guarantee full participation in the study.
- Female patients must have negative serum or urine pregnancy tests and must not be lactating. For females able to bear children, a hormonal (i.e., oral, implantable, or injectable) and single-barrier method, or a double-barrier method of birth control must be used throughout the study. A vasectomized partner will be allowed as one in conjunction with another single-barrier method.
- Female patients unable to bear children must have this documented in the case report form (i.e., tubal ligation, hysterectomy, or postmenopausal [defined as a minimum of

one year since the last menstrual period]). Post-menopausal status will be confirmed by follicle stimulating hormone (FSH) in women less than 60 years of age

4.4 Exclusion Criteria

- Unable or unwilling to provide informed consent or to comply with study procedures.
- Diagnosis of secondary constipation beyond that of PD
- Structural or metabolic diseases that affect the GI system
- Functional GI disorder
- Unable to withdraw the following medications 2 weeks prior to the dose-escalation period and throughout the study: Laxatives, opiates, sedatives, hypnotics, protein pump inhibitors or any medications which may cause constipation
- History of recent major surgery (within 60 days of screening)
- Any clinically significant abnormalities on screening laboratories or physical examination requiring further evaluation or treatment.
- Neurological disorder other than PD
- On treatment with intra-jejunal dopamine or carbidopa/levodopa (i.e. Duopa)
- Treatment with COMT inhibitors (entacapone, tolcapone, Stalevo)
- Patients starting a new PD medication or modifying an existing medication within 4 weeks prior to enrollment
- Unable to maintain a stable diet regimen
- Patients with a cognitive impairment that preclude them from understanding the informed consent
- Patients placed under legal guardianship
- Acute GI illness within 2 weeks of the baseline period
- History of major GI surgery (e.g. previous abdominal surgery, including Cholecystectomy), except that patients with uncomplicated appendectomy are allowed.
- ALT or AST > 1.5 X upper limit of normal (ULN) during screening

• Females who are pregnant or breastfeeding

• History of excessive alcohol use or substance abuse

Patient or caregiver unable to administer daily oral dosing.

• Participation in an investigational clinical study within the 6 months prior to dosing in

the present study.

• Any other reason, which in the opinion of the Investigator would confound proper

interpretation of the study.

